3.3 Adaptive Design

Not applicable.

4. Covariates and Subgroups

4.1 Planned Covariates

Region (North America versus Rest of World) and baseline migraine frequency (CM versus EM) will be included in the repeated measures linear mixed models models as stratification factors. In addition, the baseline value corresponding to the endpoint being analyzed will also include.

4.2 Subgroups

The primary and secondary endpoints may also be explored using subgroup analyses of region (North America, Rest of World), migraine frequency type (EM, CM), prior anti-CGRP medication use (Yes, No), prior migraine prophylactic treatment failure (1, \geq 2), medication overuse (Yes, No), CAP score (0, \geq 1), age (<Median, \geq Median), sex (Female, Male), race (White, Other), response status to AMG 334 (Yes, No), and other subgroup variables as deemed appropriate.

5. Definitions

5.1 Endpoints

5.1.1 Efficacy Endpoints

The baseline period for efficacy analysis is defined as the period between week -4 visit (date on which the eDiary device is set up) and the day prior to study day 1 (study day 1 is not included).

eDiary Day

A day in which a subject uses the eDiary and data are entered for that day.

Migraine Day

A migraine day is any calendar day from the eDiary in which the subject experiences a qualified migraine headache (onset, continuation or recurrence of the migraine headache). A qualified migraine headache is defined as a migraine with or without aura, lasting for ≥ 4 hours, and meeting at least one of the following criteria:

- a) ≥ 2 of the following pain features:
 - Unilateral
 - Throbbing
 - Moderate to severe
 - Exacerbated with exercise/physical activity
- b) ≥ 1 of the following associated symptoms:
 - Nausea and/or vomiting
 - Photophobia and phonophobia

If the subject took a migraine-specific medication (ie, triptan or ergotamine) during aura or to treat headache on a calendar day, then it will be counted as a migraine day regardless of the duration and pain features/associated symptoms.

Monthly Migraine Days

Number of migraine days during a 28-day period. Monthly migraine days at baseline are the number of migraine days in the baseline period. Days without eDiary data in each monthly interval are handled by proration according to [Section 8.3](#).

Headache Day

A headache day is any calendar day from the eDiary in which the subject experiences a qualified headache (initial onset, continuation or recurrence of the headache). A qualified headache is defined as:

- a qualified migraine headache (including an aura-only event that is treated with acute migraine-specific medication), or
- a qualified non-migraine headache, which is a headache that lasts ≥ 4 hours and is not a qualified migraine headache, or
- A headache of any duration for which acute headache treatment is administered.

Monthly Headache Days

Number of headache days during a 28-day period. Monthly headache days at baseline are the number of headache days in baseline period. Days without eDiary data in each monthly interval are handled by proration according to [Section 8.3](#).

Information Day

A day which is either a headache day or an eDiary day.

Migraine Attack

A migraine attack is an episode of any qualified migraine headache or migraine specific medication intakes for aura only. The following rules will be used to distinguish an attack of long duration from two attacks, or to distinguish between attacks and relapses:

- a) A migraine attack that is interrupted by sleep, or temporarily remits, and then recurs within 48 hours will be considered as one attack and not two.
- b) An attack treated successfully with medication but with relapse within 48 hours will be considered as one attack.

A migraine attack lasting more than 48 hours will be counted as one attack.

Monthly Migraine Attacks

Number of migraine attacks during each 28-day period. Monthly migraine attacks at baseline are the number of migraine attacks in baseline period. Days without eDiary data are handled by proration according to Section 8.3.

Response

At least a 50% (or at least 75% or 100%) reduction from baseline in monthly migraine days over the last 4 weeks of the DBTP.

Monthly Acute Headache Medication Treatment Days

Number of days on which acute headache medications are used as recorded in eDiary during each 28-day period. Monthly acute headache medication treatment days at baseline are the number of acute headache medication treatment days in the baseline period. Days without eDiary data are handled by proration according to [Section 8.3](#).

Monthly Acute Migraine-specific Medication Treatment Days

Number of days on which migraine specific medications are used during each 28-day period. Migraine-specific medications include two categories of medications: triptan-based migraine medications and ergotamine-based migraine medications. Monthly migraine-specific medication treatment days at baseline are the number of migraine-specific medication treatment days in the baseline period. Days without eDiary data are handled by proration according to Section 8.3.

Monthly Average Severity of Migraine Pain

Severity of migraine pain is graded as 1=mild, 2=moderate or 3=severe and is rated as its worst or peak intensity per migraine headache. The monthly average severity of migraine pain is defined as the sum of the severity of each observed qualified migraine headache during each 28-day period divided by the total number of observed qualified migraine headaches (as one record in eDiary with start and end time) in that interval. If fewer than 14 days of eDiary data in each interval is recorded, then the monthly average severity of migraine pain will be set as missing. Monthly average severity of migraine pain at baseline is the average severity of migraine pain in the baseline period.

Clinical Outcomes Assessments (COA) and Electronic Diaries (eDiaries)

The Clinical Outcomes Assessments (COAs) will be collected by subjects using a handheld eDiary at various frequencies. The eDiary will collect the following COAs daily at home:

- Date and time of start of headache (ie, migraine or non-migraine headache)
- Date and time of end of each headache
- Worst pain severity per headache
- Pain features (eg, 1-sided, throbbing, worsens with exercise/physical activity)
- Symptoms (eg, aura, nausea, vomiting, photophobia, phonophobia)
- Use of acute medications (medication name [from pre-entered list] date of dosing, number of times taken of each date, number of units taken)

The subject's eDiary will also be used for the completion of the following patient-reported outcomes (PROs) measures:

- HIT-6, monthly in clinic
- Modified MIDAS questionnaire; monthly in clinic
- MPFID, daily at home

Headache Impact Test (HIT-6)

The Headache Impact Test (HIT-6) is a short-form self-administered questionnaire based on the Internet-HIT question pool. The HIT-6 was developed as a global measure of adverse headache impact to assess headache severity in the previous month and change in a patient's clinical status over a short period of time. Six questions cover:

- severe pain,
- limitation of daily activity (household, work, school and social),
- wanting to lie down when headache is experienced,
- feeling too tired to work or do daily activities because of headache,
- feeling fed up or irritated because of headache,
- headache limiting ability to concentrate or work on daily activities.

Each of the 6 questions is responded to using 1 of 5 response categories: "never," "rarely," "sometimes," "very often," or "always."

For each HIT-6 item, 6, 8, 10, 11, or 13 points, respectively, are assigned to the response provided. These points are summed to produce a total HIT-6 score that ranges from 36 to 78. The HIT-6 score is categorized into 4 grades, representing little or no impact (49 or less), some impact (50-55), substantial impact (56-59), and severe impact (60-78) due to headache. No recall period is specified for the first 3 items. The recall period is the past 4 weeks for the last 3 items. Subjects will complete the HIT-6 using the eDiary at the clinical assessment visit. Please refer to [Appendix E](#) for scoring algorithm.

Modified Migraine Disability Assessment (MMIDAS)

The modified Migraine Disability Assessment Questionnaire (MMIDAS) is a 5-item self-administered questionnaire that sums the number of productive days lost over the past month in two settings: the workplace and the home. The MMIDAS also assesses disability in family, social, and leisure activities. The MMIDAS score is the sum of missed days due to a headache from paid work, housework, and non-work (family, social, leisure) activities; and days at paid work or housework where productivity was reduced by at least half. **The original MIDAS was a 3-month recall assessment.**

In order to categorize severity of subjects with the MMIDAS, the total score is multiplied by 3 and categorized into 4 severity grades: Grade I = 0 - 5 (defined as minimal or infrequent disability), Grade II = 6 - 10 (mild or infrequent disability), Grade III = 11 - 20 (moderate disability), and Grade IV = 21 and over (severe disability). The recall period is the past one month.

Subjects will complete the modified MMIDAS monthly using the eDiary. Please refer to [Appendix E](#) for scoring algorithm.

Migraine Physical Function Impact Diary (MPFID)

The MPFID is a self-administered 13-item instrument measuring physical functioning. It has 2 domains, Impact on Everyday Activities (7 items) and Physical Impairment (5 items), and 1 stand-alone global question that provides an assessment of the overall impact of migraine on subjects' everyday activities. The recall period for each item is the past 24 hours.

Subjects respond to items using a 5-point scale, with difficulty items ranging from "Without any difficulty" to "Unable to do" and frequency items ranging from "None of the time" to "All of the time". These are assigned scores from 1 to 5, with 5 representing the greatest burden. For each domain, the scores will be calculated as the sum of the item responses and the sum will be rescaled to a 0 to 100 scale, with higher scores representing greater impact of migraine (ie, higher burden). There will be a score for each of the 2 domains and a third score for the stand-alone item.

The recall period is the past 24 hours.

Please refer to [Appendix E](#) for more information.

Subjects will complete the MPFID every day using the eDiary.

Monthly Days with Impairment as Measured by MPFID

If $\geq 50\%$ of the 13 daily items are completed, this is the number of days with a response of 3, 4, or 5 on any item of the MPFID between each monthly IP dose. Monthly days with impairment at baseline is the number of impairment days during the baseline period. Days with $< 50\%$ of the 13 daily items completed are handled by proration according to [Section 8.3](#).

Monthly Days with Physical Impairment as Measured by MPFID Physical Impairment (PI) Domain

If $\geq 50\%$ of the daily items within the PI domain are completed, this is the number of days with a response of 3, 4, or 5 on any of the 5 daily items on the PI domain between

each monthly IP dose. Monthly days with physical impairment at baseline is the number of impairment days during the baseline period. Days with < 50% of the 5 daily items in the PI domain completed are handled by proration according to [Section 8.3](#).

Monthly Day with Impact on Everyday Activities as Measured by MPFID Everyday Activities (EA) Domain

If ≥ 50% of the daily items within the EA domain are completed, this is the number of days with a response of 3, 4, or 5 on any of the 7 daily items on the EA domain between each monthly IP dose. Monthly days with impact on everyday activities at baseline is the number of impairment days during the baseline period. Days with < 50% of the 7 daily items in the EA domain completed are handled by proration according to Section 8.3.

Achievement of at least a 50% reduction from baseline in monthly migraine days over the last 4 weeks of the DBTP

Calculated based on the following: if (monthly migraine days over the last 4 weeks of the DBTP - baseline monthly migraine days) * 100 / baseline monthly migraine days is less than or equal to - 50%

Change from baseline in monthly acute migraine-specific medication treatment days over the last 4 weeks of the DBTP

Calculated based on the following: (monthly acute migraine-specific medication treatment days over the last 4 weeks of the DBTP) – (baseline monthly acute migraine-specific medication treatment days)

Change from baseline in monthly average physical impairment scores as measured by the MPFID over the last 4 weeks of the DBTP

Calculated based on the following: (monthly average physical impairment scores as measured by the MPFID over the last 4 weeks of the DBTP) – (baseline monthly average physical impairment scores as measured by the MPFID)

Change from baseline in monthly average impact on everyday activities scores as measured by the MPFID over the last 4 weeks of the DBTP

Calculated based on the following: (monthly average impact on everyday activities scores as measured by the MPFID over the last 4 weeks of the DBTP) – (baseline monthly average impact on everyday activities scores as measured by the MPFID)

Achievement of at least a 5-point reduction from baseline in monthly average impact on everyday activities/physical impairment domain scores over the last 4 weeks of the DBTP

The achievement of at least a 5-point reduction from baseline in monthly average impact on everyday activities/physical impairment domain scores as measured by the MPFID is calculated based on the following:

If (monthly average impact on everyday activities/physical impairment domain score over the last 4 weeks of the DBTP - baseline monthly average impact on everyday activities/physical impairment domain score) is less than or equal to -5

Cranial Autonomic Parasympathetic Symptom (CAPS) Scale

The CAPS Scale is a 5-item questionnaire that assesses whether migraine subjects experience each of the following 5 CAPS based on the ICHD, third edition beta (ICHD-IIIb), with headaches: 1) lacrimation, 2) conjunctival injection, 3) eyelid edema, 4) sensation of fullness in the ear and 5) nasal congestion and/or rhinorrhea. Each CAPS (eg, consider all headaches experienced over the past 4 weeks) is graded as either 0 (absent), 1 (present but mild) or 2 (present and conspicuous). The CAPS total score ranges from 0 to 10 points. ([Riesco et al, 2016](#)).

The CAPS scale will be administered by clinical study center staff as described in Table 2-1 of the protocol.

5.1.2 Safety Endpoints

Treatment-emergent Adverse Event (TEAE)

An adverse Event (AE) recorded on the Events eCRF page that occurs on or after the date of the first dose of investigational product (IP), as determined by the flag indicating the event did not start before first dose of IP on the Events eCRF, and up to and including **126 days** after the end of IP (ie. **18 weeks** after the last dose of IP).

Serious TEAE

A serious treatment-emergent adverse event is an SAE considered to be treatment-emergent.

Disease-Related Event (DRE)

Disease-related Events (DREs) are events determined by the flag on the Event CRF.

Columbia-Suicide Severity Rating Scale (C-SSRS)

The C-SSRS is a clinician rating of suicidal behavior and ideation. Two versions depending on the type of visits will be used in this study: Screening and Since Last Visit. The C-SSRS consists of a maximum of 20 items, which defines 5 subtypes of suicidal ideation and behavior in addition to self-injurious behavior with no suicidal intent. The C-SSRS will be administered by the principal investigator or qualified designee to evaluate suicidal behavior and suicidal ideation. For the baseline assessment, for measurements with multiple individual items, all individual items from the same set of measurement will be used for analysis.

For C-SSRS, the last complete assessment prior to first IP administration will be used as the baseline. If subject completes C-SSRS form on Day 1 then all individual items from Day 1 visit will be used as baseline. If subject does not complete C-SSRS form on Day 1 then all individual items from Week -4 visit will be used as baseline. Please refer to [Appendix E](#) for more information.

Beck Depression Inventory (BDI)-II

The BDI-II is a 21-item questionnaire that assesses severity of depression. Each item is scored from 0 to 3. The total score is categorized into 4 severity grades: Minimal depression (0-13), mild depression (14-19), moderate depression (20-28) and severe depression (29-63). Please refer to Appendix E for more information.

5.2 Study Dates

Informed Consent Date

The date on which subject signs the informed consent form.

eDiary Device Assignment Date

The date on which an eDiary device is assigned to a subject for the first time after completion of initial screening at week -4 visit and which is the beginning of the baseline period.

Enrollment Date

The date on which the investigator decides that the subject has met all Part 1 and Part 2 eligibility criteria. The subject is also randomized per IVRS on this date.

Randomization Date

Randomization date is the date on which a subject is assigned to one of the treatments through the Interactive Voice Response System (IVRS). The randomization date is the same as the enrollment date.

First IP Dose Date

The first IP dose date is the date on which a subject is administered the first dose of IP following randomization, which may be the same day or after the randomization date. For subjects who are randomized but not dosed with double-blind IP after randomization, the first IP dose date is considered missing.

Last IP Dose Date

The last IP dose date for each subject is defined as the latest date IP is administered.

End of IP Admin Date

The end of IP admin date for each subject is defined as the date the decision was made to end IP as recorded on the End of IP eCRF page.

Subject-level End of Study (EOS) Date

The end of study (EOS) date for each subject is defined as the last date on which the subject participated in the study. The date will be recorded on the End of Study eCRF page.

Subject-level End of Double Blind (EODB) Treatment Phase Date

The end of double blind (EODB) treatment phase date for each subject is defined as the last date on which the subject participated in the double-blind treatment phase. The date will be recorded on the End of Double Blind eCRF page.

Study Completion Date (Study-level EOS Date)

The study completion date is the date when the last subject is assessed or receives an intervention for evaluation in the study (ie, when the last subject completes the study, which includes the safety follow-up visit 18 weeks after the last dose of IP, or is discontinued from the study).

5.3 Study Points of Reference

Baseline Period

The 4-week baseline period starts when the subject has met all Part 1 eligibility criteria (refer to Section 6.1 of the protocol) and is entered in the baseline period (refer to Section 6.6 of the protocol) and ends when the subject is considered a screen failure (discontinuation before randomization and/or subject does not meet all baseline eligibility criteria, refer to [Section 6.3](#)) or randomized.

The first day of the baseline period is the day that the subject records the first assessment in the eDiary and the last day of this period is the date the subject records the last assessment prior to the first dose of IP on Study Day 1.

The baseline assessment is defined as the last non-missing measurement for the endpoint of interest taken before the first dose of IP. In cases where baseline measurements are taken on the same day as the first dose of IP, it will be assumed that these measurements are taken prior to IP being administered. For subjects who are randomized but not dosed after the randomization, the baseline of the study is defined as the last non-missing measurement prior to or on the date of randomization. Above definition applies to safety measurements and PROs collected at office **visits** (HIT-6, CAPS and MMIDAS).

For measurements with multiple individual items such as C-SSRS and ECG, all individual items from the same set of measurement will be used for analysis. If some items from the same set are missing, then the latest complete set of measurement prior to the first dose of IP will be used as baseline. A similar rule holds for post-baseline measurements.

Baseline assessment of data collected from eDiary will be summarized as monthly measurements using data collected during baseline period.

Study Day 1

Study Day 1 is defined as the first IP dose date. For subjects who are randomized but not dosed after randomization, the Study Day 1 is defined as the date of randomization.

Study Day

Study Day is defined as the number of days from Study Day 1.

Before Study Day 1:

Study Day = (date of interest – date of Study Day 1)

On or after Study Day 1:

Study Day = (date of interest – date of Study Day 1) + 1

Therefore the day prior to Study Day 1 is -1.

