9.6.6 Columbia Suicide Severity Rating Score (C-SSRS)

No statistical testing will be performed on C-SSRS. The number and percentage of subjects in each of the 5 categories describing suicidal behavior and ideation will be summarized by treatment group.

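### SAP 5.3 extends its complete-form rule to post-baseline C-SSRS without protecting positive answers, so a positive answer on a partly completed form can drop out of the C-SSRS summary

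*SAP*

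**What the plan says.** The multi-item paragraph of SAP 5.3 begins "For measurements with multiple individual items such as C-SSRS and ECG" and requires that all items come from one form. For a form with gaps it continues: "If some items from the same set are missing, then the latest complete set of measurement prior to the first dose of IP" is taken as baseline. The next sentence is the whole of the post-baseline provision: "A similar rule holds for post-baseline measurements".

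The other passages that bear on the C-SSRS are these.

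- SAP 5.1.2 on the instrument: "Two versions depending on the type of visits will be used in this study: Screening and Since Last Visit". On its length: "The C-SSRS consists of a maximum of 20 items".
- SAP 5.1.2 on form handling is limited to baseline: "For the baseline assessment, for measurements with multiple individual items, all individual items from the same set of measurement will be used for analysis". It gives no post-baseline rule, so nothing there overrides 5.3.
- SAP 9.6.6 on the output: "The number and percentage of subjects in each of the 5 categories describing suicidal behavior and ideation" are tabulated by treatment group. It does not say whether the count is by visit, at worst, or at any time after baseline.
- The note after the SAP 5.4 window tables picks, among non-missing visits in one window, the one nearest the target day.
- SAP 8.3 leaves missing safety data unimputed, apart from adverse event dates.

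The other example named in 5.3, the ECG, is not summarised (SAP 9.6.8). The C-SSRS is therefore the named instrument that the sentence actually reaches.

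**The concern.** Preferring a complete form does little harm when choosing a baseline value. After baseline it does not suit this instrument, for two reasons.

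First, each answered item is informative by itself. Protocol 9.2.3.5.1 treats ideation of severity 4 or 5, or any attempt or preparatory behaviour, as enough to mark a subject as high risk. The SAP 9.6.6 summary counts categories and does not sum a score, so a blank elsewhere on the form does not invalidate a positive answer.

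Second, a Since Last Visit form describes its own interval. Another visit's form cannot say what happened in that interval.

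Few events are to be expected, because exclusion criteria 219 and 237 keep out subjects with severity 4 or 5 ideation or any suicidal behaviour at screening and baseline. Losing even one positive would visibly change a sparse table, and SAP 9.6.6 is the only planned summary of this scale.

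**Working it through.** The plan gives no figure to reproduce. The check traces the rule through the text and then adds one labelled illustration.

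**Trace.** Take a subject with forms at weeks 4, 8 and 12 (target days 29, 57 and 85 in SAP Table 5-2). Weeks 4 and 12 are complete and negative. Week 8 has a positive ideation item and one blank item.

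| How the post-baseline rule is applied | What week 8 contributes | Counted for ideation at any post-baseline time? |
|---|---|---|
| Look back to the latest complete form | Week 4 answers, nominally 57 − 29 = 28 days earlier | No |
| Complete form from the same window only (days 44 to 71), no imputation | Missing, unless a complete unscheduled form falls in the window | No, unless that unscheduled form is itself positive |
| Every answered item counts | The week 8 answers | Yes |

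The positive answer is lost under both complete-set applications. Another interval's answers stand in for it only under the first.

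**Does other text rescue it?** SAP 5.1.2 covers baseline only. The 5.4 note chooses between visits and does not address a form with gaps. SAP 8.3 forbids filling in but does not say that a partial form is kept. SAP 9.6.6 has no worst-case or any-positive rule. None of these retains the answer.

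**Direction.** For an any-time count, discarding a positive form can only lower the total, provided that any replacement is itself a post-baseline form. For a by-visit count under look-back the effect can also go up: an earlier complete positive form would replace a later incomplete negative one and repeat the positive at the later visit.

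**Illustration.** Suppose three subjects each have one positive post-baseline form, and each such form is incomplete with probability q, independently. The chance that at least one is lost is 1 − (1 − q)³.

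- q = 0.01: 1 − 0.99³ = 1 − 0.970299 = 0.0297, about 3%.
- q = 0.05: 1 − 0.95³ = 1 − 0.857375 = 0.1426, about 14%.

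The three subjects, the independence and the range of q are all assumptions. The documents give neither an expected number of positives nor a rate of blank items.

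**The case against.** The strongest reply is that the SAP does not state a carry-forward at all. It says only that the post-baseline rule is similar. That could mean no more than taking all items from one form without mixing, in which case the partial form would stay in. SAP 8.3 and the same-window selection in 5.4 both count against moving a form between intervals. This stands in part. A reader might infer from 5.3 that an earlier interval's form is certain to be substituted, and the documents do not support that, because no source window is named. But the sentence directly follows the replacement rule for incomplete sets, which is its natural antecedent, and a programmer could reasonably apply it that way. Even the milder same-window application loses the positive.

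A reader might also infer that a complete form has no fixed meaning because the number of items varies. The public text cannot settle this. SAP 5.1.2 refers to Appendix E, which is redacted and may define it, and items skipped by design need not count as missing.

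Thirdly, the form is administered by a clinician, so gaps may be rare. That is fair, and it is one reason why no size is claimed.

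Finally, the investigator acts on a positive report at the site (protocol 9.2.3.5.1). Clinically significant findings on safety assessments meet the adverse event definition in protocol Appendix 4 and are tabulated under SAP 9.6.2. This stands in full: neither route depends on the 5.3 rule.

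**Conclusion.** The point holds as a gap in the rule. SAP 5.3 extends complete-set handling to post-baseline C-SSRS forms without an exception for positive answers and without naming where a replacement comes from. Under either complete-set application, a positive answer on a partial form leaves the SAP 9.6.6 table. Under look-back, answers from another interval may take its place, in tension with 8.3 and 5.4.

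The likely effect is to understate any-time post-baseline counts. It would be too strong to say that the rule can only hide positives: 9.6.6 does not fix the type of count, and the trace shows that look-back can raise a by-visit figure. The size is unknown; 3% to 14% is an illustration that rests on the assumptions stated with it. The consequence is confined to one descriptive, untested table. A reader might infer that suicidal-risk monitoring of subjects is weakened, and the documents do not support that.

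**What to change.** - In SAP 5.3, limit the complete-set rule to the baseline assessment, or state that it does not apply to post-baseline C-SSRS forms.
- In SAP 9.6.6, count a subject as positive in a category if any answered item for that category is positive on any post-baseline form, whether or not the form is complete.
- State that a Since Last Visit form is never carried into another interval, which brings 5.3 into line with 8.3.

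The cost is a few sentences of SAP text and a small programming change. No new data are needed.
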